1. BACKGROUND INFORMATION AND STUDY RATIONALE

Parkinson's disease is a relatively common neurodegenerative disorder characterised by motor symptoms such as poorness and slowness of movement, tremors and loss of balance. Psychiatric symptoms such as anxiety and depression as well as other non-motor symptoms are also common. The disorder is associated with a markedly increased risk of developing dementia [1]. Treatments that restore dopamine deficits in the brain such as levodopa and dopamine agonists have been used since the 1970s to treat the motor symptoms in Parkinson's disease. However, it has long been known that after a few years of initial motor normalisation, such drugs frequently cause adverse effects [2, 3]. Adverse effects on motor symptoms such as wearing-off, on-off and dyskinesias limit the usefulness of current approved drug treatments, prompting the use of device treatments such as deep brain stimulation and infusion pumps for patients in more advanced stages of disease.

It is estimated that within five years of initiation of standard dopamine replacement therapy in Parkinson's disease (PD), about 50% of patients (and after 10 years almost all patients) develop involuntary movements:- so called Levodopa Induced Dyskinesias (LIDs), in response to their medical treatment [4]. LIDs are often the key complication that limits further dose increases in dopaminergic therapy.

There is increasing recognition that non-motor symptoms, such as Parkinson's disease Psychosis (PDP) are burdensome to PD patients. Paranoid delusions result in patient distress and behavioural disturbance; visual or auditory hallucinations are more frequent. PD patients with cognitive impairment are prone to develop hallucinations, i.e. psychotic symptoms, in response to dopaminergic treatments [5]. In a systematic review of clinical populations the prevalence of hallucinations alone was between 21% and 46% [6].

The key pathophysiology of PD involves loss of dopaminergic and noradrenergic innervation. Other cortical, subcortical and autonomic pathologies contribute to the non-motor symptoms of the disorder [7]. It has been suggested that cortico-striatal dys-connectivity and plasticity are key drivers for both the core symptoms of PD as well as for the adverse effects emerging with long standing dopaminergic treatment [8]

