4.3. Exclusion criteria

Patients must not enter the study if any of the following exclusion criteria are fulfilled:

1. History of neurosurgical intervention related to Parkinson's disease (e.g. deep brain stimulation).
2. Treatment with pump delivered antiparkinsonian therapy (i.e. subcutaneous apomorphine or levodopa/carbidopa intestinal infusion).
3. History of seizures within two years prior to screening.
4. History of stroke or transient ischemic attack (TIA) within two years prior to screening.
5. History of cancer within five years prior to screening, with the following exceptions: adequately treated non-melanomatous skin cancers, localised bladder cancer, non-metastatic prostate cancer or in situ cervical cancer.

6. Presence of cognitive impairment, as evidenced by a Mini-Mental Status Examination (MMSE) score of less than 24 during screening.
7. A Hoehn and Yahr stage of five.
8. Any history of a significant heart condition or cardiac arrhythmias within the past 5 years, any repolarisation deficits or any other clinically significant abnormal ECG as judged by the Investigator
9. Severe or ongoing unstable medical condition including a history of poorly controlled diabetes; obesity associated with metabolic syndrome; uncontrolled hypertension; cerebrovascular disease, or any form of clinically significant cardiac disease, clinically significant symptomatic orthostatic hypotension; clinically significant hepatic disease, renal failure or abnormal renal function (definition of abnormal renal function is creatinine clearance <45 ml/min (calculated according to the Cockcroft-Gault formula).
10. Any history of a neurological other than Parkinson's disease or a psychiatric disorder, including history of DSM IV diagnosed major depression or psychosis. Patients with illusions or hallucinations with no loss of insight will be eligible. Patients with mild depression who are well controlled on a stable dose of an antidepressant medication for at least 4 weeks before screening will be eligible.
11. Enrolment in any other clinical study involving medication, medical devices or surgical procedures, current or within three months prior to screening visit, or previous participation in the present study. Patients enrolled in non-interventional clinical trials will be eligible.
12. Drug and/or alcohol abuse.
13. History of severe drug allergy or hypersensitivity.
14. If female, is pregnant or lactating, or has a positive pregnancy test result pre-dose.

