11.9. Efficacy Analyses

All Primary, Secondary and Exploratory endpoints (except CGI) can be considered quantitative continuous data (Interval in type). As such the Change from baseline at and at End of Treatment (Visit 4, Day 28 or earlier in the event of withdrawal) will be derived for each patient and analysed using an Analysis Of Covariance (ANCOVA) model to compare the two treatment groups (IRL790 vs Placebo).

The ANCOVA analysis will allow estimation of the size of treatment effects as well as magnitude of differences between the active treatment and control (IRL790 - Placebo). The dependent variable will be the Change from baseline value and Treatment group the explanatory (independent) variable and fixed factor. A baseline covariate term will be included to ensure minimum variance unbiased estimation.

In view of the small sample size and relatively large number of sites there are insufficient degrees of freedom to include Site as a factor in the model.

Model assumptions will be investigated and a suitable data transformation or non-parametric equivalent model substituted if appropriate.

Actual p-values and 95% confidence intervals for least square mean estimates of the treatment effects and differences from placebo will be presented for these models.

The CGI exploratory endpoint is the only other type of data collected. This qualitative and ordinal categorical variable will be analysed using the Van Elteren non parametric hypothesis test (equivalent to Cochran Mantel-Haenszel test with modified ridits (CMH-row mean scores differ). Statistical significance (p-values) for differences between the two Treatment groups (IRL790, Placebo) will be reported together with the actual response proportions.

11.10.Safety Analyses

Safety evaluations include: Adverse events and Concomitant medications reporting, Complete physical examination, Vital signs, ECG (12 lead) at rest and Clinical safety laboratory tests (clinical chemistry, haematology and coagulation).

Adverse events and concomitant medications are recorded throughout the investigational period with the rest performed at Screening, Day 28 (Visit 4 or at Withdrawal) and Follow-up (5-8 days after Visit 4).

All safety laboratory samples are assayed at the local hospital.

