1.1 COGNITIVE IMPAIRMENT

Instructions to examiner: Consider all types of altered level of cognitive function including cognitive slowing, impaired reasoning, memory loss, deficits in attention and orientation. Rate their impact on activities of daily living as perceived by the patient and/or caregiver.

Instructions to patients [and caregiver]: Over the past week have you had problems remembering things, following conversations, paying attention, thinking clearly, or finding your way around the house or in town? [If yes, examiner asks patient or caregiver to elaborate and probes for information]

- 0: Normal: No cognitive impairment.
- 1: Slight: Impairment appreciated by patient or caregiver with no concrete interference with the patient's ability to carry out normal activities and social interactions.
- 2: Mild: Clinically evident cognitive dysfunction, but only minimal interference with the patient's ability to carry out normal activities and social interactions.
- 3: Moderate: Cognitive deficits interfere with but do not preclude the patient's ability to carry out normal activities and social interactions.
- 4: Severe: Cognitive dysfunction precludes the patient's ability to carry out normal activities and social interactions.

SCORE

1.2 HALLUCINATIONS AND PSYCHOSIS	SCORE

Instructions to examiner: Consider both illusions (misinterpretations of real stimuli) and hallucinations (spontaneous false sensations). Consider all major sensory domains (visual, auditory, tactile, olfactory and gustatory). Determine presence of unformed (for example sense of presence or fleeting false impressions) as well as formed (fully developed and detailed) sensations. Rate the patients insight into hallucinations and identify delusions and psychotic thinking.
 
Instructions to patients [and caregiver]: Over the past week have you seen, heard, smelled or felt things that were not really there? [If yes, examiner asks patient or caregiver to elaborate and probes for information]
 
0: Normal: No hallucinations or psychotic behaviour.
 
1: Slight: Illusions or non-formed hallucinations, but patient recognizes them without loss of insight.
 
2: Mild: Formed hallucinations independent of environmental stimuli. No loss of insight
 
3: Moderate: Formed hallucinations with loss of insight.
 
4: Severe: Patient has delusions or paranoia.
	

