3.1.5 Exploratory endpoints

Additionally, a number of exploratory end points will be assessed. The following items will be assessed:

- Unified Parkinson's Disease Rating Scale (MDS-UPDRS), part I (total score), part II (total score), part III (total score) and part IV (total score) from Baseline (Day 1) to Visit 4 (Day 28).
- Unified Parkinson's Disease Rating Scale (MDS-UPDRS) Question 1.2 (Hallucinations and Psychosis) from Baseline (Day 1) to Visit 4 (Day 28).
- Unified Parkinson's Disease Rating Scale (MDS-UPDRS) Question 1.6 (Features of dopamine dysregulation syndrome) from Baseline (Day 1) to Visit 4 (Day 28).
 - Change in sum score of Questions 4.3, 4.4 and 4.5 (motor fluctuations) in MDS-UPDRS part IV to Visit 4 (Day 28).
 - Change in sum score of Questions 3.15 and 3.16 (postural and kinetic tremor of the hands) in MDS-UPDRS part III to Visit 4 (Day 28).
- Unified Parkinson's Disease Rating Scale (MDS-UPDRS) Question 4.3 (Time spent in the off state) from Baseline (Day 1) to Visit 4 (Day 28).
- Unified Parkinson's Disease Rating Scale (MDS-UPDRS) Question 4.6 (Painful off state dystonia) from Baseline (Day 1) to Visit 4 (Day 28).
- UDysRS part 1 (Historical on-dyskinesia)
- UDysRS part 2 (Historical off-dystonia)
- UDysRS part 1+2 (Historical dyskinesia)
- Change in "ON" time with troublesome dyskinesia as assessed by patient completed 24hour diaries, from run-in to Visit 4 (Day 28).
- Change in "ON" time as assessed by patient completed 24-hour diaries, from run-in to Visit 4 (Day 28).
- Change in Sleep time as assessed by patient completed 24-hour diaries, from run-in to Visit 4 (Day 28).

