7.3 Exploratory Endpoints

- 7.3.1 Definitions
- Unified Parkinson's Disease Rating Scale (MDS-UPDRS), part I (total score), part II (total score), part III (total score) and part IV (total score) from Baseline (Day 1) to Visit 4 (Day 28).
- Unified Parkinson's Disease Rating Scale (MDS-UPDRS) Question 1.2 (Hallucinations and Psychosis) from Baseline (Day 1) to Visit 4 (Day 28).
- Unified Parkinson's Disease Rating Scale (MDS-UPDRS) Question 1.6 (Features of dopamine dysregulation syndrome) from Baseline (Day 1) to Visit 4 (Day 28).
 - Change in sum score of Questions 4.3, 4.4 and 4.5 (motor fluctuations) in MDS-UPDRS part IV to Visit 4 (Day 28).
 - Change in sum score of Questions 3.15 and 3.16 (postural and kinetic tremor of the hands) in MDS-UPDRS part III to Visit 4 (Day 28).
- Unified Parkinson's Disease Rating Scale (MDS-UPDRS) Question 4.3 (Time spent in the off state) from Baseline (Day 1) to Visit 4 (Day 28).
- Unified Parkinson's Disease Rating Scale (MDS-UPDRS) Question 4.6 (Painful off state dystonia) from Baseline (Day 1) to Visit 4 (Day 28).
- Clinician's Global Impression of Change in overall PD symptoms at Visit 4 (Day 28).
- Change in "ON" time with troublesome dyskinesia as assessed by patient completed 24hour diaries, from run-in to Visit 4 (Day 28).
- Change in "ON" time as assessed by patient completed 24-hour diaries, from run-in to Visit 4 (Day 28).
- Change in Sleep time as assessed by patient completed 24-hour diaries, from run-in to Visit 4 (Day 28).

The change from baseline will be defined as both absolute and percent change.

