7.3.2 Analyses

The Exploratory endpoints (except CGI) can be considered quantitative continuous data (Interval in type). As such the Change from baseline to End of Treatment (Visit 4, Day 28 or earlier in the event of withdrawal) will be derived for each patient and analysed using an Analysis Of Covariance (ANCOVA) model to compare the two treatment groups (IRL790 vs Placebo).

The ANCOVA analysis will allow estimation of the size of treatment effects as well as magnitude of differences between the active treatment and control (IRL790 - Placebo). The dependent variable will be the Change from baseline value and Treatment group the explanatory (independent) variable and fixed factor. A baseline covariate term will be included to ensure minimum variance unbiased estimation.

Model assumptions will be investigated, and a suitable data transformation or non-parametric equivalent model substituted if appropriate.

Actual p-values and 95% confidence intervals for least square mean estimates of the treatment effects (including differences between active treatment and placebo) will be presented for these models.

The CGI will be analysed using Chi-square test without continuity correction.

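### Item 1.2 (hallucinations and psychosis) is analysed only as a mean absolute and percent change; a shift table and a count of scores of 3 or above should be added

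*Protocol*

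**What the plan says.** Item 1.2 is an exploratory endpoint in Protocol 2.2 and 11.7 (Table 3) and in SAP 3.1.5 and 7.3.1. Protocol 11.9 states: "All Primary, Secondary and Exploratory endpoints (except CGI) can be considered quantitative continuous data (Interval in type"). SAP 7.3.2 repeats this for its own list: "The Exploratory endpoints (except CGI) can be considered quantitative continuous data (Interval in type"). Both then fit an ANCOVA of change on treatment with a baseline covariate. Both allow a transformation or a non-parametric substitute, but give no trigger for it. SAP 7.3.1 adds: "The change from baseline will be defined as both absolute and percent change".

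Protocol Appendix 2 defines the item. Scores 1 and 2 describe illusions or hallucinations with insight kept. The next level is "3: Moderate: Formed hallucinations with loss of insight", and 4 is delusions or paranoia.

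Exclusion criterion 10 (Protocol 4.3) bars a history of psychosis but adds: "Patients with illusions or hallucinations with no loss of insight will be eligible". The study schedule scores only MDS-UPDRS question 4.1 at screening.

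Under SAP 4.4, continuous data get at least n, mean, SD, median, minimum and maximum; frequencies are for categorical data. No frequency by score level, shift table or count at a threshold is planned for item 1.2. The one scale that Protocol 11.9 exempts from interval treatment is the CGI: "This qualitative and ordinal categorical variable will be analysed using the Van Elteren non parametric hypothesis test".

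**The concern.** A mean counts a step from 1 to 0 as equal and opposite to a step from 2 to 3. The first is the end of a mild symptom; the second is loss of insight. One summary number therefore nets benefit in some patients against harm in others.

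That mixture is plausible here. Protocol 1.1 and 1.1.1 attribute antipsychotic effects to IRL790 and name Parkinson's disease psychosis as a second intended indication. Improvement in mild hallucinations is thus a hoped-for effect, and the result for this item is one that later development may cite.

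The percent change raises a separate problem. It has no value for a patient who starts at 0, so a patient who goes from 0 to 3 drops out of that analysis.

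**Working it through.** **Plan's own figure.** The documents give no figure for item 1.2. The only planning figure is 37 per group for the UDysRS total (effect size 0.67, 80% power, two-sided 0.05). A two-sample t-test needs 36 per arm and has 81.1% power at 37, so the figure is reproduced. Here it supplies only the arm size.

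**Baseline range (assumption).** Protocol section 1 cites a prevalence of hallucinations of 21% to 46% in clinical populations. Taken as the share scoring 1-2 at baseline, that is 0.21 × 37 = 7.8 to 0.46 × 37 = 17.0 patients per arm. The example uses 25 patients at 0, 7 at 1 and 5 at 2 in each arm (12/37 = 32%), with placebo unchanged.

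**Weight of one case.** One patient going from 0 to 3 moves the arm mean by 3/37 = 0.081. Three patients move it by 9/37 = 0.243.

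**Room to cancel.** Patients at 1-2 can improve by at most 7 × 1 + 5 × 2 = 17 points, enough to cancel five such cases in full (5 × 3 = 15). With a 29/5/3 baseline the room is 5 + 6 = 11 points, enough for three.

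**ANCOVA of absolute change, three active patients going from 0 to 3:**
- No one else changes: difference +0.24 (95% CI -0.03 to 0.51, p = 0.08).
- Five active patients with baseline 2 improve by nine points in total (four by 2, one by 1): difference 0.00 (95% CI -0.33 to 0.33, p = 1.00).

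**Percent change, same second case.** The 25 patients per arm at baseline 0 have no value. The remaining 12 active patients average (4 × -100% + 1 × -50% + 7 × 0%)/12 = -37.5%, against 0% on placebo. This analysis favours the drug, and all three new cases are missing from it.

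**Count, either case.** Scores of 3 or above: 3/37 = 8.1% (exact 95% CI 1.7% to 21.9%) versus 0/37; Fisher p = 0.24.

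**How often this happens.** Simulation of 4,000 trials per row, 37 per arm. Assumed: 8% of active and no placebo patients newly at 3; baseline scores 1 and 2 in the ratio 60:40; improvement by 1 point.

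| Baseline 1-2 | Improving, active vs placebo | Mean difference | p<0.05 towards harm | Zero or favours drug |
|---|---|---|---|---|
| 21% | 50% vs 20% | +0.17 | 11.6% | 9.9% |
| 46% | 50% vs 20% | +0.07 | 3.2% | 31.5% |
| 46% | 70% vs 20% | -0.02 | 0.5% | 57% |

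With equal improvement (20% in both arms) the mean difference is +0.19 to +0.23, and ANCOVA is significant towards harm in about 24% to 28% of trials.

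**The case against.** The case on the other side is strong, and most of it stands.

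- **The entry range does not cause the averaging.** A reader might infer that, because patients enter at 0-2, new psychosis must average out. It does not follow. Cancellation needs more improvement on active than on placebo, and without it the mean moves towards harm. With equal improvement ANCOVA is the more sensitive test: about 24% to 28% of trials significant towards harm, against 6% to 8% for Fisher's test on the count. The range is also only implied by exclusion 10, so a Visit 4 score of 3 is not certain to be new unless baseline is shown.
- **Psychosis would not go unseen.** A reader might infer that it would. But SAP 7.5.5 tabulates adverse events by patient, preferred term, seriousness and severity. The DSMB sees unblinded adverse events (Protocol 23). SAP 4.4 gives maxima and patient listings. What is missing is a summary of this endpoint by level.
- **The count is not a better test.** It exceeds placebo in about 95% of the simulated trials, but only because placebo was set to zero: 1 - 0.92^37 = 95.4%. At this sample size its value is descriptive.
- **An ordinal test is not the answer.** The way CGI is treated in Protocol 11.9 may suggest a Van Elteren test. In the three scenarios of the table, stratified by baseline (0 versus 1-2), it is zero or favours the drug in 29% to 81% of trials, against 10% to 55% for ANCOVA in the same comparison. Ranks discount a jump from 0 to 3 and still net improvement against worsening. The non-parametric clause in SAP 7.3.2 has the same limit.

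None of this supplies the missing breakdown by level or gives percent change a value at baseline 0.

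**Conclusion.** The point holds as a minor one on an exploratory endpoint. The planned analyses of item 1.2 can show a mean difference near zero while several active patients newly lose insight, but only if the drug also improves mild hallucinations more than placebo does. The psychosis and improvement rates used here are assumptions. The 21% to 46% is background prevalence before this trial's exclusions, not a trial figure.

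The percent-change defect needs no assumption about drug effect: every patient with baseline 0 is lost from that analysis. If the background range applied, that would be 54% to 79% of patients (100% minus 46% and 21%).

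The documents do not support the stronger conclusions that the eligibility rule hides psychosis or that the trial would miss it.

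**What to change.** In SAP 7.3.1 and 7.3.2, before unblinding:

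1. For item 1.2, add a shift table of baseline score by Visit 4 score for each arm, using the end-of-treatment assessment for patients who withdraw early and showing missing scores as their own column.
2. Report the number and percentage per arm with a Visit 4 score of 3 or above, with exact 95% confidence intervals. Show each such patient's baseline score so that new cases can be identified. Read the result alongside the psychiatric adverse events.
3. Drop percent change for items 1.2 and 1.6, and give a shift table for item 1.6 as well.
4. Keep ANCOVA of absolute change as a secondary summary if wanted. Do not replace it with a Van Elteren test as the remedy.

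The cost is a few lines of SAP text and two descriptive tables on data already collected; the SAP already has a generic layout for categorical data (Table 12.1-1). Only the percent-change output for these two items is lost.

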4.1 TIME SPENT WITH DYSKINESIAS

SCORE

Instructions to examiner: Determine the hours in the usual waking day and then the hours of dyskinesias. Calculate the percentage. If the patient has dyskinesias in the office, you can point them out as a reference to ensure that patients and caregivers understand what they are rating. You may also use your own acting skills to enact the dyskinetic movements you have seen in the patient before or show them dyskinetic movements typical of other patients. Exclude from this question early morning and nighttime painful dystonia.

Instructions to patient [and caregiver]. Over the past week, how many hours do you usually sleep on a daily basis, including nighttime sleep and daytime napping? Alright, if you sleep ___ hrs, you are awake ___ hrs. Out of those awake hours, how many hours in total do you have wiggling, twitching or jerking movements? Do not count the times when you have tremor, which is a regular back and forth shaking or times when you have painful foot cramps or spasms in the early morning or at nighttime. I will ask about those later. Concentrate only on these types of wiggling, jerking and irregular movements. Add up all the time during the waking day when these usually occur. How many hours ____ (use this number for your calculation).

- | | | |
|--------------|-------------------------|---------------------------------------|
| 0: Normal: | No dyskinesias. | |
| 1: Slight: | ≤ 25% of waking day. | 1. Total Hours Awake: _____ |
| 2: Mild: | 26 - 50% of waking day. | 2. Total Hours with Dyskinesia: _____ |
| 3: Moderate: | 51 - 75% of waking day. | 3. % Dyskinesia = ((2/1)*100): _____ |
| 4: Severe: | > 75% of waking day. | |

Copyright © 2008 Movement Disorder Society. All rights reserved.
This chart may not be copied, distributed or otherwise used in whole or in part without prior written consent of the Movement Disorder Society.

4.2 FUNCTIONAL IMPACT OF DYSKINESIAS	SCORE						

Instructions to examiner: Determine the degree to which dyskinesias impact on the patient's daily function in terms of activities and social interactions. Use the patient's and caregiver's response to your question and your own observations during the office visit to arrive at the best answer.
 
Instructions to patient [and caregiver]: Over the past week, did you usually have trouble doing things or being with people when these jerking movements occurred? Did they stop you from doing things or from being with people?
 
0: Normal: No dyskinesias or no impact by dyskinesias on activities or social interactions.
 
1: Slight: Dyskinesias impact on a few activities, but the patient usually performs all activities and participates in all social interactions during dyskinetic periods.
 
2: Mild: Dyskinesias impact on many activities, but the patient usually performs all activities and participates in all social interactions during dyskinetic periods.
 
3: Moderate: Dyskinesias impact on activities to the point that the patient usually does not perform some activities or does not usually participate in some social activities during dyskinetic episodes.
 
4: Severe: Dyskinesias impact on function to the point that the patient usually does not perform most activities or participate in most social interactions during dyskinetic episodes.
							
B . MOTOR FLUCTUATIONS							

4.3 TIME SPENT IN THE OFF STATE
 
Instructions to examiner: Use the number of waking hours derived from 4.1 and determine the hours spent in the "OFF" state. Calculate the percentage. If the patient has an OFF period in the office, you can point to this state as a reference. You may also use your knowledge of the patient to describe a typical OFF period. Additionally you may use your own acting skills to enact an OFF period you have seen in the patient before or show them OFF function typical of other patients. Mark down the typical number of OFF hours, because you will need this number for completing 4.6
 
Instructions to patient [and caregiver]: Some patients with Parkinson's disease have a good effect from their medications throughout their awake hours and we call that "ON" time. Other patients take their medications but still have some hours of low time, bad time, slow time or shaking time. Doctors call these low periods "OFF" time. Over the past week, you told me before that you are generally awake ____ hrs each day. Out of these awake hours, how many hours in total do you usually have this type of low level or OFF function ____ (Use this number for your calculations).
 
0: Normal: No OFF time.
 
1: Slight: ≤ 25% of waking day.
 
2: Mild: 26 - 50% of waking day.
 
3: Moderate: 51 - 75% of waking day.
 
4: Severe: > 75% of waking day.
							

 
 	1. Total Hours Awake: _____	
 
 	2. Total Hours OFF: _____	
 
 	3. % OFF = ((2/1)*100): _____	
 
			1. Total Hours Awake: _____		2. Total Hours OFF: _____		3. % OFF = ((2/1)*100): _____
	1. Total Hours Awake: _____						
	2. Total Hours OFF: _____						
	3. % OFF = ((2/1)*100): _____						

Copyright © 2008 Movement Disorder Society. All rights reserved.
This chart may not be copied, distributed or otherwise used in whole or in part without prior written consent of the Movement Disorder Society.

4.4 FUNCTIONAL IMPACT OF FLUCTUATIONS	SCORE

Instructions to examiner: Determine the degree to which motor fluctuations impact on the patient's daily function in terms of activities and social interactions. This question concentrates on the difference between the ON state and the OFF state. If the patient has no OFF time, the rating must be 0, but if patients have very mild fluctuations, it is still possible to be rated 0 on this item if no impact on activities occurs. Use the patient's and caregiver's response to your question and your own observations during the office visit to arrive at the best answer.
 
Instructions to patient [and caregiver]: Think about when those low or "OFF" periods have occurred over the past week. Do you usually have more problems doing things or being with people than compared to the rest of the day when you feel your medications working? Are there some things you usually do during a good period that you have trouble with or stop doing during a low period?
 
0: Normal: No fluctuations or No impact by fluctuations on performance of activities or social interactions.
 
1: Slight: Fluctuations impact on a few activities, but during OFF, the patient usually performs all activities and participates in all social interactions that typically occur during the ON state.
 
2: Mild: Fluctuations impact many activities, but during OFF, the patient still usually performs all activities and participates in all social interactions that typically occur during the ON state.
 
3: Moderate: Fluctuations impact on the performance of activities during OFF to the point that the patient usually does not perform some activities or participate in some social interactions that are performed during ON periods.
 
4: Severe: Fluctuations impact on function to the point that, during OFF, the patient usually does not perform most activities or participate in most social interactions that are performed during ON periods.
	

4.5 COMPLEXITY OF MOTOR FLUCTUATIONS
 
Instructions to examiner: Determine the usual predictability of OFF function whether due to dose, time of day, food intake or other factors. Use the information provided by the patients and caregiver and supplement with your own observations. You will ask if the patient can count on them always coming at a special time, mostly coming at a special time (in which case you will probe further to separate slight from mild), only sometimes coming at a special time or are they totally unpredictable? Narrowing down the percentage will allow you to find the correct answer.
 
Instructions to patient [and caregiver]: For some patients, the low or "OFF" periods happen at certain times during day or when they do activities like eating or exercising. Over the past week, do you usually know when your low periods will occur? In other words, do your low periods always come at a certain time? Do they mostly come at a certain time? Do they only sometimes come at a certain time? Are your low periods totally unpredictable?"
 
0: Normal: No motor fluctuations.
 
1: Slight: OFF times are predictable all or almost all of the time (> 75%).
 
2: Mild: OFF times are predictable most of the time (51-75%).
 
3: Moderate: OFF times are predictable some of the time (26-50%).
 
4: Severe: OFF episodes are rarely predictable. (≤ 25%).
	

Copyright © 2008 Movement Disorder Society. All rights reserved.
This chart may not be copied, distributed or otherwise used in whole or in part without prior written consent of the Movement Disorder Society.

C. "OFF" DYSTONIA

